Significance level and power: The procedure described above test the null hypothesis that the response rate is 15% versus alternating hypotheses that the response rate is 35%. The significance level (*i.e.*, the probability of rejecting H0 when it is true) is α =0.05 and the power (*i.e.*, the probability of deciding the regimen is active) is 0.81 when true response rate is 20%. The expected sample size with this design is 19 when the null hypothesis is true and 25 when the alternative hypothesis is true.

Dose Escalation Schedule			
	Dose		
Dose Level	itraconazole (mg)	hydroxychloroquine (mg)	
Level -1	300 mg PO BID	200 mg PO OD	
Level 1	300 mg PO BID	200 mg PO BID	
Level 2	300 mg PO BID	400 mg PO BID	
Level 3	300 mg PO BID	600mg PO BID	

TABLE OF CONTENTS

SCF	HEMA	3
SYN	NOPSIS	5
1.	OBJECTIVES	10

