13.1.2 Phase II study design

Once the dose level for hydroxychloroquine and combination itraconazole has been determined, the cohort will be expanded in a single-centre, single-arm, Simon two-stage design.

The phase II cohort will consist of a maximum of additional 34 patients. If 1 response is observed after 9 patients have been treated at RP2D, then an additional 25 patients will be enrolled.

CT scans will be performed every 8 weeks regardless of dosing delays.

The phase II cohort will serve to investigate ORR based on RECIST criteria (refer to).

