13.2 Sample Size/Accrual Rate

The sample size will be a maximum of 52 patients. This will encompass between 6 and 18 on phase I and 34 on for the phase II component.

Phase II sample size:

Stage 1 of accrual: 9 response evaluable patients will be entered in the first stage. Using response hypotheses of H_0 <15 % and H_a >35%, we would reject the drug at the end of the first stage of accrual if no objective responses were seen. Otherwise, an additional 25 patients will be accrued. Patients treated at RP2D in the phase 1 part of the study will be considered for the statistical analysis of the phase 2 stage 1. A total (between phase 1 and phase 2 stage 1) of 9 response evaluable patients treated at RP2D are required.

Stage 2 of accrual: An additional 25 patients will be accrued. We would accept the drug as active if 8 or more objective responses are observed from 25 patients accrued.

Significance level and power: The procedure described above test the null hypothesis that the response rate is 15% versus alternating hypotheses that the response rate is 35%. The significance level (*i.e.*, the probability of rejecting H0 when it is true) is α =0.05 and the power (*i.e.*, the probability of deciding the regimen is active) is 0.81 when true response rate is 20%. The expected sample size with this design is 19 when the null hypothesis is true and 25 when the alternative hypothesis is true.

Accrual and Duration of Study

The estimated accrual for this study is 2-4 patients a month. Thus, patient accrual is expected to be completed within 12-18 months. Additional time is required to allow the response data to mature.

All of the patients registered in the study will be accounted for. The number of patients who were not evaluable, who died or withdrew before treatment began will be specified. The distribution of follow-up time will be described and the number of patients lost to follow-up will be given.

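### The final phase II success rule counts only the 25 stage-2 patients and, with the printed stage-1 rule, has alpha 0.020 and power 0.680, not the stated 0.05 and 0.81; both boundaries need reconciling

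*Protocol*

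**What the plan says.** Section 13.1.2 calls phase II a single-arm Simon two-stage design. Section 13.2 and the Statistics part of the Synopsis give the same details.

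- **Hypotheses:** "Using response hypotheses of H_0 <15 % and H_a >35" per cent, restated later as a null rate of 15% against 35%.
- **Stage 1:** "9 response evaluable patients will be entered in the first stage", and patients already treated at the RP2D in phase I count towards the nine.
- **Stage-1 stop:** "we would reject the drug at the end of the first stage of accrual if no objective responses were seen". Section 13.1.2 puts it the other way round: "If 1 response is observed after 9 patients have been treated at RP2D, then an additional 25 patients will be enrolled".
- **Stage 2:** otherwise "an additional 25 patients will be accrued".
- **Final rule:** "We would accept the drug as active if 8 or more objective responses are observed from 25 patients accrued".
- **Stated properties of this procedure:** alpha 0.05; power 0.81, printed as applying at a true rate of 20%; expected sample size 19 under the null and 25 under the alternative.

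No section states a final threshold over all 34 patients.

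**The concern.** The final decision of a Simon design is made on the responses of both stages together. Here the printed denominator is the 25 stage-2 patients, so responses among the first nine would open the gate to stage 2 and then drop out of the count. That includes responses in the RP2D patients from phase I, whom the protocol deliberately brings into stage 1.

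The protocol attributes its alpha and power to this same procedure: "test the null hypothesis that the response rate is 15% versus alternating hypotheses that the response rate is 35" per cent. If the rule and its stated properties do not belong together, two readers can draw opposite conclusions from the same data. For example, 5 of 9 followed by 7 of 25 is 12 of 34, or 35%, the target rate itself. It fails the printed rule and passes a cumulative threshold of 8 or 9.

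**Working it through.** **Inputs** (section 13.2, repeated in the Synopsis): p0 = 0.15, p1 = 0.35, n1 = 9, n2 = 25, stop at 0 of 9, accept at 8 or more of 25. Let X1 ~ Bin(9, p) and X2 ~ Bin(25, p), independent.

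**Step 1. Which design gives the stated figures?** For a cumulative rule, P(accept) = Σ P(X1 = x) · P(X2 ≥ c − x), summed over the stage-1 counts x that continue. An exhaustive search for p0 = 0.15, p1 = 0.35, alpha ≤ 0.05 and power ≥ 0.80 returns as the optimal design: stop at 1 or fewer of 9, accept at 9 or more of 34. Its alpha is 0.0474 and its power 0.811. Its null expected sample size follows from:

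- P(X1 ≤ 1 | 0.15) = 0.85^9 + 9 · 0.15 · 0.85^8 = 0.2316 + 0.3679 = 0.5995
- E(N) = 9 + 25 · (1 − 0.5995) = 19.0

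These are the protocol's 0.05, 0.81 and 19.

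**Step 2. The rule as printed.** P(accept) = P(X1 ≥ 1) · P(X2 ≥ 8).

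- At 15%: (1 − 0.2316) · 0.02547 = 0.0196
- At 35%: (1 − 0.0207) · 0.6939 = 0.680

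**Step 3. Other readings.**

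| Stage-1 stop | Accept at | Alpha (15%) | Power (35%) |
|---|---|---|---|
| 0 of 9 (printed) | ≥ 8 of the 25 (printed) | 0.020 | 0.680 |
| none applied | ≥ 8 of the 25 | 0.025 | 0.694 |
| 0 of 9 | ≥ 8 of 25 in total (9 + 16) | 0.025 | 0.691 |
| 0 of 9 | ≥ 8 of 34 | 0.121 | 0.933 |
| 0 of 9 | ≥ 9 of 34 | 0.057 | 0.880 |
| 0 of 9 | ≥ 10 of 34 | 0.023 | 0.797 |
| ≤ 1 of 9 | ≥ 8 of 34 | 0.095 | 0.850 |
| ≤ 1 of 9 | ≥ 9 of 34 | 0.047 | 0.811 |

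Among these, only the last row has the stated alpha and power.

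**Step 4. How often the denominator matters.** Any trial that passes the printed rule has at least 1 + 8 = 9 responses in 34. With the printed stage-1 stop and a true rate of 35%, the chance of reaching 9 of 34 but failing 8 of 25 is therefore 0.880 − 0.680 = 0.20.

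**Step 5. The remaining printed figures.**

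- *Power at 20%.* The printed rule has power 0.094 there. The design in step 1 has 0.188. Neither is 0.81.
- *Expected sample size, stop at 0 of 9.* Under the null it is 9 + 25 · (1 − 0.2316) = 28.2. At 35% it is 9 + 25 · (1 − 0.0207) = 33.5.
- *Expected sample size, stop at 1 or fewer of 9.* At 35% the stopping probability is 0.0207 + 9 · 0.35 · 0.65^8 = 0.0207 + 0.1004 = 0.1211, so E(N) = 9 + 25 · 0.8789 = 31.0.
- The stated 25 under the alternative matches neither stopping rule.

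**The case against.** The strongest reply is that the 25 is a drafting slip and that everyone will pool the stages. The design is named as Simon two-stage, RP2D patients from phase I are counted in stage 1, and section 13.5.2 requires conclusions to rest on all eligible patients. This makes a cumulative count the likelier intention, so 0.020 and 0.680 describe the literal text and perhaps not what would be done. It does not rescue the plan: pooling with the printed threshold of 8 and the printed stage-1 stop gives alpha 0.121, more than twice the stated 0.05.

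A reader might infer that it is enough to replace the final rule by 9 or more of 34. With the printed stop at 0 of 9 that gives 0.057 and 0.880, with a null expected sample size of 28.2. It would turn a conservative test into one that exceeds its nominal level.

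A reader might also take the design in step 1 as proven to be the intended one. It is inferred. Three of the protocol's figures fit it, but the expected 25 under the alternative and the 20% attached to the power do not, and the protocol nowhere states those boundaries.

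Finally, it is tempting to call this the trial's only efficacy decision. The stage-1 stop is another, and response rate is a secondary endpoint. The primary endpoint, the maximum tolerated or administered dose, is untouched.

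**Conclusion.** The point holds. The printed final rule and its printed properties do not belong together: 0.020 and 0.680 against 0.05 and 0.81 on the literal reading, 0.121 and 0.933 if pooled at 8 of 34. The agreement of alpha, power and null expected size with a stop at 1 or fewer of 9 and acceptance at 9 or more of 34 suggests that both boundaries were miscopied. Only the sponsor can confirm that.

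The figures assume independent responses with a common rate, exactly 9 and 25 response-evaluable patients, and that section 13.1.2 means at least one response. Because the protocol itself fixes boundary, denominator, alpha and power, and they conflict, this is not a detail that can be left to a later analysis plan. Response rate is secondary, but it is the quantity that sizes phase II and decides whether the regimen is called active, so the rule must be corrected.

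**What to change.** The sponsor's statistician should settle the following together, in one amendment, before response data are reviewed:

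1. the stage-1 boundary (Synopsis, 13.1.2, 13.2);
2. the final threshold and its denominator (Synopsis, 13.2);
3. the operating characteristics (Synopsis, 13.2).

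There are two coherent routes. One is to correct both boundaries to the design that has the stated properties: stop at 1 or fewer of 9, active at 9 or more of all 34 (alpha 0.047, power 0.811, null expected size 19.0). The other is to keep the printed boundaries, state the denominator beyond doubt, and report the true figures: 0.020 and 0.680 if the 25 is meant, 0.121 and 0.933 if the 34 is meant, with a null expected size of 28.2.

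On either route, attach the power to a true rate of 35% instead of 20%, and correct the expected size under the alternative to 31.0 (stop at 1 or fewer) or 33.5 (stop at 0).

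The cost is an amendment to several places. The maximum of 34 patients stays. If the stop at 1 or fewer of 9 is adopted, the chance of ending after stage 1 rises from 0.232 to 0.599 at a true 15%, and from 0.021 to 0.121 at a true 35%.

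### Phase II power of 0.81 is attached to a true response rate of 20%, which is neither hypothesis, and the expected sample size of 25 under the alternative does not reproduce

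*Protocol*

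**What the plan says.** Protocol section 13.2 (Sample Size/Accrual Rate), repeated in the Statistics part of the synopsis, says that the phase II procedure will "test the null hypothesis that the response rate is 15"% "versus alternating hypotheses that the response rate is 35"%. Alpha is given as "the probability of rejecting H0 when it is true) is α =0.05". Power is then said to be the chance of declaring the regimen active, and it "is 0.81 when true response rate is 20"%. The expected sample size is given as 19 under the null "and 25 when the alternative hypothesis is true".

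The rule to which these figures are attached is as follows:

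- Stage 1: "9 response evaluable patients will be entered in the first stage", and "we would reject the drug at the end of the first stage of accrual if no objective responses were seen". Otherwise 25 more patients are added, 34 in all. Section 13.1.2 likewise continues on 1 response in 9.
- Stage 2: the drug is accepted on 8 or more responses, worded as counted among the 25 patients then accrued.

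**The concern.** A true rate of 20% is neither the null nor the alternative. It lies 5 points above the null, and a design of 34 patients could not have power of 0.81 there at alpha 0.05. Taken at face value, the sentence would let a negative phase II result count as good evidence against a 20% response rate.

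The expected size of 25 also looks too low. If 35% is the true rate, stage 1 will rarely stop, so the mean should lie close to 34. An understated figure tells an ethics board or monitoring committee that fewer patients will be treated, on average, with an active regimen than the rule implies.

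**Working it through.** **Inputs** (section 13.2): p0 = 0.15, p1 = 0.35, n1 = 9, n2 = 25, n = 34, stop at 0 of 9, accept at 8 or more. Sidedness is not stated; a Simon test is one-sided.

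**Formulas.** With stage 1 stopping at r1 or fewer responses:

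- PET(p) = P(Bin(9, p) ≤ r1)
- E[N] = 9 + 25 × (1 − PET)
- Acceptance at k or more of all 34: the sum over x > r1 of P(Bin(9, p) = x) × P(Bin(25, p) ≥ k − x)
- Acceptance at 8 or more of the stage 2 patients only: (1 − PET) × P(Bin(25, p) ≥ 8)

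**Reproducing the plan's figures first.** A search over Simon designs for 15% v 35%, alpha 0.05 and power at least 0.80, with total size up to 39, gives the smallest expected size under the null to 1/9, 8/34. That means stop at 1 or fewer of 9 and accept at 9 or more of 34.

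- Alpha 0.0474 (stated 0.05).
- Power at 35% 0.8107 (stated 0.81).
- PET at 15% = 0.85^9 + 9 × 0.15 × 0.85^8 = 0.5995, so E[N] = 9 + 25 × 0.4005 = 19.01 (stated 19).

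Three stated figures match this design, and its 0.81 belongs to 35%.

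**Expected size under the alternative.**

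- Stop at ≤1 of 9: PET at 35% = 0.65^9 + 9 × 0.35 × 0.65^8 = 0.1211; E[N] = 9 + 25 × 0.8789 = 30.97.
- Stop at 0 of 9, as written: PET = 0.65^9 = 0.0207; E[N] = 9 + 25 × 0.9793 = 33.48.

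The stated 25 is low by about 6.0 or 8.5 patients. A value near 25 appears only if the total is 25 (9 + 16, stop at 0 of 9: 24.7), which contradicts 34, or at true rates of 20% to 25% with the ≤1 of 9 rule (23.1 to 26.5), which are not the alternative.

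**Power at 20% and the other characteristics, by rule.**

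| Rule | Alpha at 15% | Power at 20% | Power at 35% | E[N] at 15% | E[N] at 35% |
|---|---|---|---|---|---|
| Written, literal: stop at 0/9; ≥8 of the 25 stage 2 patients | 0.0196 | 0.0945 | 0.6795 | 28.2 | 33.5 |
| Written stage 1; ≥8 of 34 | 0.1208 | 0.3527 | 0.9329 | 28.2 | 33.5 |
| Simon optimal: stop at ≤1/9; ≥9 of 34 | 0.0474 | 0.1877 | 0.8107 | 19.0 | 31.0 |
| Stated | 0.05 | 0.81 | not given | 19 | 25 |

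The literal figure at 20%, for example, is (1 − 0.1342) × 0.1091 = 0.0945.

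**Other readings tried at 20%.** Stop at 0/9 with ≥9 of 34 gives 0.221; stop at ≤1/9 with ≥8 of 34 gives 0.286; a single stage accepting at ≥8 of 34 gives 0.367. Even a cut-off of 7 of 34 with the written stage 1 gives only 0.504. Treating 20% as a remnant of a 5% v 20% design does not help: with 9 + 25 and stop at 0/9, power at 20% is 0.827 with cut-off 4 (alpha 0.067) or 0.760 with cut-off 5 (alpha 0.021).

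**The case against.** The strongest reply is that this is a slip that an attentive reader will catch. The sentence before gives 15% against 35%, and the stage 1 text repeats both rates. Response rate is a secondary endpoint, since the primary one is the maximum tolerated or administered dose. The expected sample size enters no decision rule, the maxima of 34 and 52 are stated, and some of the first 9 patients may come from phase I, so expected size is not purely additional exposure. All of this stands and limits the harm. It does not make the two figures correct, and both appear wherever the operating characteristics are given.

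Three stronger readings are tempting and are not supported:

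- A reader might infer that the trial's real power at 20% is 0.19. That figure belongs to the Simon optimal design, whose boundaries the protocol does not contain. That this design was intended is a strong inference, because it reproduces three stated figures, but the document does not say so. The written rule gives 0.09 or 0.35.
- A reader might infer that 34 patients are too few. They are not: 34 is the correct size for 15% v 35% at about 80% power under the optimal boundaries.
- A reader might infer that restating the figures is enough. It is not, because the replacement figures depend on which boundaries apply.

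**Conclusion.** The point holds for two figures. Power of 0.81 is attached to the wrong rate: at 20% exact power is 0.09, 0.35 or 0.19 depending on the rule, and no reading approaches 0.81. Expected size under the alternative is 31.0 (stop at ≤1/9) or 33.5 (stop at 0/9, as written), not 25.

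The results are exact binomial calculations. They assume that the decision rule is followed as specified and that stage 1 and stage 2 hold 9 and 25 response-evaluable patients. The size justification itself is not undermined. What cannot stand is a paragraph whose figures come partly from a design other than the one it describes.

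**What to change.** In the synopsis and section 13.2:

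1. Replace 20% with 35% as the rate at which power is stated.
2. Reconcile the written boundaries with the quoted figures, and carry the result into section 13.1.2. State whether the final count is over all 34 patients or only the 25 of stage 2.
3. Restate every operating characteristic for the boundaries kept:
   - If 1/9, 8/34 is adopted (stop at ≤1 of 9, accept at ≥9 of 34): alpha 0.047, power 0.81 at 35%, expected size 19 under the null and 31 under the alternative.
   - If the stop at 0 of 9 is kept: expected size 28 and 33.5, with alpha 0.12 and power 0.93 at 35% (≥8 of 34), or alpha 0.02 and power 0.68 (≥8 of 25).

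The cost is a protocol amendment and no extra patients. Step 2 is a real choice. Moving the stage 1 stop from 0 to ≤1 of 9 raises the chance of stopping early from 23% to 60% at a true 15%, and from 2% to 12% at a true 35%. The figures in step 3 should not be inserted until that choice is made.

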13.2.1 Patient Replacement

If a patient is withdrawn from the study prior to completing 28 days of therapy without experiencing a DLT prior to withdrawal, an additional patient may be added to that dose level. Patients missing 7 or more days due to toxicity will not be replaced since these patients will be considered to have experienced a dose limiting toxicity.

13.3 Stratification Factors

No stratification will be used for this trial.

13.4 Analysis of Secondary Endpoints

Summary statistics, such as mean, median, counts and proportion, will be used to summarize the patients. Survival estimates will be computed using the Kaplan-Meier method. Potential association between variables will be measured using Pearson correlation coefficients, chi-square tests, one- or two-sample t-tests or logistic regression analyses as appropriate. Non-parametric tests such as Spearman correlation coefficients, Fisher's exact tests and Wilcoxon rank sum test may be substituted if necessary. Ninety-five percent confidence intervals will be constructed and selected results will be illustrated using figures and plots.

Frequency and severity of adverse events will be tabulated using counts and proportions detailing frequently occurring, serious and severe events of interest.

13.5 Reporting and Exclusions

13.5.1 Evaluation of Toxicity

All patients will be evaluable for toxicity from the time of their first treatment with itraconazole and hydroxychloroquine.

13.5.2 Evaluation of Response

All patients included in the study must be assessed for response to treatment, even if there are major protocol treatment deviations or if they are ineligible. Each patient will be assigned one of the following categories: 1) complete response, 2) partial response, 3) stable disease, 4) progressive disease, 5) early death from malignant disease, 6) early death from toxicity, 7) early death because of other cause, or 9) unknown (not assessable, insufficient data). [Note: By arbitrary convention, category 9 usually designates the "unknown" status of any type of data in a clinical database.]

All of the patients who met the eligibility criteria (with the possible exception of those who received no study medication) should be included in the main analysis of the response rate. Patients in response categories 4-9 should be considered to have a treatment failure (disease progression). Thus, an incorrect treatment schedule or drug administration does not result in exclusion from the analysis of the response rate. Precise definitions for categories 4-9 will be protocol specific.

All conclusions should be based on all eligible patients. Subanalyses may then be performed on the basis of a subset of patients, excluding those for whom major protocol deviations have been identified (*e.g.*, early death due to other reasons, early discontinuation of treatment, major protocol violations, etc.). However, these subanalyses may not serve as the basis for drawing conclusions concerning treatment efficacy, and the reasons for excluding patients from the analysis should be clearly reported. The 95% confidence intervals should also be provided.

REFERENCES

- 1. Navaneelan, T., *Trends in the incidence and mortality of female reproductive system cancers. Health at a Glance.* Statistics Canada catalogue 201. **no. 82-624-X.**
- 2. Fung-Kee-Fung, M., et al., *Optimal chemotherapy treatment for women with recurrent ovarian cancer*. Curr Oncol, 2007. **14**(5): p. 195-208.
- 3. Tania, M., M.A. Khan, and Y. Song, *Association of lipid metabolism with ovarian cancer*. Curr Oncol, 2010. **17**(5): p. 6-11.
- 4. Pyragius, C.E., et al., *Aberrant lipid metabolism: an emerging diagnostic and therapeutic target in ovarian cancer.* Int J Mol Sci, 2013. **14**(4): p. 7742-56.
- 5. Hedditch, E.L., et al., *ABCA transporter gene expression and poor outcome in epithelial ovarian cancer.* J Natl Cancer Inst, 2014. **106**(7).

APPENDIX A PERFORMANCE STATUS CRITERIA

ECC	OG Performance Status Scale	K	Earnofsky Performance Scale
Grade	Descriptions	Percent	Description
0	Normal activity. Fully active, able to carry on all pre-disease	100	Normal, no complaints, no evidence of disease.
U	performance without restriction.	90	Able to carry on normal activity; minor signs or symptoms of disease.
1	Symptoms, but ambulatory. Restricted in physically strenuous activity, but ambulatory and able	80	Normal activity with effort; some signs or symptoms of disease.
1	to carry out work of a light or sedentary nature (e.g. , light housework, office work).	70	Cares for self, unable to carry on normal activity or to do active work.
2	In bed <50% of the time. Ambulatory and capable of all self-care, but unable to carry out	60	Requires occasional assistance, but is able to care for most of his/her needs.
	any work activities. Up and about more than 50% of waking hours.	50	Requires considerable assistance and frequent medical care.
3	In bed >50% of the time. Capable of only limited self-care, confined	40	Disabled, requires special care and assistance.
3	to bed or chair more than 50% of waking hours.	30	Severely disabled, hospitalization indicated. Death not imminent.
4	100% bedridden. Completely disabled. Cannot carry on any	20	Very sick, hospitalization indicated. Death not imminent.
4	self-care. Totally confined to bed or chair.	10	Moribund, fatal processes progressing rapidly.
5	Dead.	0	Dead.

APPENDIX C PROHIBITED DRUGS

alfentanil

avanafil

budesonide

buspirone

conivaptan

dapsone

darifenacin

darunavir

dasatinib

dronedarone

ebastine

eletriptan

eplerenone

everolimus

felodipine

ibrutinib

indinavir

lomitapide

lovastatin

lurasidone

maraviroc

midazolam

naloxegol

nisoldipine

quetiapine

saquinavir

sildenafil

simvastatin

sirolimus

tacrolimus

ticagrelor

tipranavir

tolvaptan

triazolam

Vardenafi

Other antimalaria agents

Drugs with Known Torsades de	Drugs with Possible Torsades
Pointes risk	the Pointes risk
Amiodarone	Alfuzosin
Anagrelide	Apomorphine
Arsenic trioxide	Aripiprazole
Astemizole	Artenimol+piperaquine
Azithromycin	Asenapine
Bepridil	Atomoxetine
Chloroquine	Bedaquiline
Chlorpromazine	Bendamustine
Cilostazol	Bortezomib
Ciprofloxacin	Bosutinib
Cisapride	Buprenorphine
Citalopram	Capecitabine
Clarithromycin	Ceritinib
Cocaine	Clomipramine
Disopyramide	Clozapine
Dofetilide	Crizotinib
Domperidone	Cyamemazine
Dompendone	(cyamepromazine)
Donepezil	Dabrafenib
Dronedarone	Dasatinib
Droperidol	Degarelix
Erythromycin	Delamanid
Escitalopram	Desipramine
Flecainide	Dexmedetomidine
Fluconazole	Dolasetron
Gatifloxacin	Efavirenz
Grepafloxacin	Eribulin mesylate
Halofantrine	Ezogabine (Retigabine)
Haloperidol	Famotidine
Ibogaine	Felbamate
Ibutilide	Fingolimod
Levofloxacin	Flupentixol
Levomepromazine	Gemifloxacin
Levomethadyl acetate	Granisetron
Levosulpiride	Hydrocodone
Mesoridazine	lloperidone
Methadone	Imipramine
Moxifloxacin	Isradipine
Ondansetron	Ketanserin

Oxaliplatin Lapatinib Papaverine HCl (Intra-coronary) Lenvatinib Pentamidine Leuprolide Pimozide Lithium Probucol Melperone Procainamide Midostaurin Propofol Mifepristone Quinidine Mirabegron Roxithromycin Mirtazapine Sevoflurane Moexipril/HCTZ Sotalol Necitumumab Sparfloxacin Nicardipine Sulpiride Nilotinib Sultopride Norfloxacin Terfenadine Nortriptyline Terlipressin Nusinersen Terodiline Ofloxacin Thioridazine Osimertinib Vandetanib Oxytocin Paliperidone Panobinostat Pasireotide Pazopanib Perflutren Perphenazine Pilsicainide Pimavanserin Pipamperone Promethazine Prothipendyl Ribociclib Rilpivirine Risperidone Romidepsin Saquinavir Sertindole Sorafenib Sunitinib Tacrolimus Tamoxifen Telavancin

Telithromycin
Tetrabenazine
Tiapride
Tizanidine
Tolterodine
Toremifene
Trimipramine
Tropisetron
Vardenafil
Vemurafenib
Venlafaxine
Vorinostat
Zotepine

These lists are not exhaustive and the user should contact a frequently updated medical/drug information reference

